7.5.2 Drug Disposal and Destruction

Celgene (or designee) will review with the investigator and relevant site personnel the process for investigational product return, disposal, and/or destruction including responsibilities for the site versus Celgene (or designee).

7.6 Investigational Product Compliance

Luspatercept will be administered as a subcutaneous injection at the clinical site by the study staff. Monitoring for subject compliance with the treatment regimen on the luspatercept arm is therefore unnecessary.

Epoetin alfa may also be self-administered by the subject at certain timepoints if certain requirements are met as further detailed [Section 7.2.2.1](#). Compliance of self-administration of epoetin alfa will be monitored via the use of a medication diary card or other local procedures in place at the investigational site.

The investigator or designee is responsible for accounting for all IP (luspatercept and epoetin alfa) that is administered during the course of the study.

Accurate recording of all IP administration will be made in the appropriate section of the subject's eCRF and source documents.

8 CONCOMITANT MEDICATIONS AND PROCEDURES

Over the course of this study, additional medications may be required to manage aspects of the disease state of the subjects, including side effects from trial treatments or disease progression. Supportive care may be administered at the discretion of the investigator.

All prior/ concomitant medications, used 8 weeks prior to randomization until 42 days after the last dose of IP, must be reported on the eCRF. All prior procedures within the 8 weeks prior to randomization as well as concomitant procedures will be recorded on the appropriate eCRF. All transfusions will be reported on the eCRF for at least 16 weeks prior to randomization until 8 weeks after last dose of IP or the EOT Visit, whichever occurs later.

Prior anticancer treatments should be recorded on the appropriate eCRF(s) regardless of treatment discontinuation/procedure date.

Prior iron chelation therapy should be recorded on the appropriate eCRF(s) regardless of treatment discontinuation date.

If a subject requires treatment with any new medications that are specifically excluded in [Section 8.2](#), the subject will be discontinued from treatment and should complete the EOT visit and enter the Post-treatment Follow-up Period of the study. The investigator should consult the medical monitor regarding any questions about whether a new medication or dosage of existing medication would require the subject to discontinue from the study.

For information regarding other drugs that may interact with IP and affect its metabolism, pharmacokinetics, or excretion, please see the Investigator's Brochure and/or local package insert.

8.1 Permitted Concomitant Medications and Procedures

8.1.1 RBC Transfusions

Concurrent treatment for anemia with blood transfusions is allowed, at the discretion of the investigator, for low hemoglobin levels, symptoms associated with anemia (eg, shortness of breath, fatigue etc.) or comorbidity.

For any RBC transfusions received during the study, hemoglobin values just prior to transfusion will be collected. Please refer to [Section 6.4.1](#) for details on required data collection.

Each subject will have a "pre-transfusion hemoglobin threshold" for requiring a transfusion during the study which will be determined based on transfusion history. Baseline pre-transfusion hemoglobin threshold will be the mean of all documented pre-transfusion hemoglobin values during the 8 weeks prior to the first dose of IP. During treatment, if the pre-transfusion hemoglobin level is increased by ≥ 1 g/dL (0.6 mmol/L) (at the time of a next anticipated transfusion event) compared to the pre-transfusion hemoglobin threshold for that subject, transfusion should be delayed by a minimum of 7 days. Subjects may be transfused at the investigator's discretion for symptoms related to anemia or other requirements (eg, infection).

8.1.2 Iron Chelation Therapy

Subjects who are using iron-chelating therapies at time of randomization should be on a stable or decreasing dose for at least 8 weeks.

Concurrent treatment with iron chelation therapies during the Treatment Period is allowed at the discretion of the investigator and is recommended to be used per product label.

8.1.3 Corticosteroids

Concurrent systemic corticosteroids used for medical conditions other than MDS is allowed provided the subject is on a stable or decreasing dose for ≥ 1 week prior to randomization. Use of topical steroids is permitted. Occasional use of corticosteroids before transfusions to prevent allergic reactions is permitted.

8.1.4 Attenuated Vaccines

Administration of attenuated vaccines (eg, influenza vaccine) is allowed if clinically indicated, per investigator discretion with the exception of a live COVID-19 vaccine.

Administration of a live COVID-19 vaccine is prohibited within 4 weeks prior to randomization. Live COVID-19 vaccines should not be used during the study, including the treatment period and until 42 days following the last dose of IP.

8.1.5 Phlebotomy

Phlebotomy may be performed for emergency/urgency if excessively high Hgb levels occur.

8.2 Prohibited Concomitant Medications and Procedures

Best supportive care for this study specifically excludes cancer surgery, immunotherapy, biologic therapy, radiotherapy, and systemic chemotherapy where the goal is to eradicate or slow the progression of the disease.

The following concomitant medications are specifically excluded during the course of the study:

- Erythropoietin stimulating agents (ESAs) other than assigned IP and other RBC hematopoietic growth factors (eg, Interleukin-3)
- Granulocyte colony stimulating factors (ie, G-CSF, GM-CSF), except in cases of neutropenic fever.
- Cytotoxic, chemotherapeutic, targeted or investigational agents/therapies
- Azacitidine, decitabine or other hypomethylating agents
- Lenalidomide, thalidomide and other immunomodulating drugs (IMiDs)
- Hydroxyurea
- Androgens, unless to treat hypogonadism
- Oral retinoids (topical retinoids are permitted)
- Arsenic trioxide
- Interferon and interleukins

8.3 Required Concomitant Medications and Procedures

Not applicable.

9 STATISTICAL CONSIDERATIONS

9.1 Overview

This is a Phase 3, multicenter, randomized, open-label, active-controlled study. The primary objective of the study is to evaluate efficacy in the two treatment arms, luspatercept compared with epoetin alfa, for the treatment of anemia due to IPSS-R very low, low, or intermediate risk MDS in ESA naïve subjects who require RBC transfusions.

The final analysis will be performed when all randomized subjects have completed 24 weeks of treatment or discontinued before 24 weeks.

Additional follow-up analysis for efficacy and safety will be performed when all subjects have been followed for 5 years from the date of the first dose of IP, or 3 years from last dose (whichever occurs later) during the Post-treatment Follow-up Period of the study.

The design of the study, including the proposed targeted subject population, study endpoints, and statistical plan, is discussed below.

9.2 Study Population Definitions

Study populations to be analyzed are defined as follows:

Intent-to-treat (ITT): The ITT population will consist of all randomized subjects regardless of whether or not the subject received IP.

Safety: The safety population will consist of all subjects who were randomized and received at least one dose of IP. Subjects will be included in the treatment group corresponding to the IP they actually received.

HRQoL evaluable population: The HRQoL evaluable population will consist of all subjects in the ITT population who completed the respective patient reported outcomes (PRO) assessment³ at baseline and at least one post-baseline assessment visit.

PK population: The PK population will consist of all subjects who received at least one dose of luspatercept and had measurable luspatercept serum concentrations.

Statistical methods to handle missing data will be described in the statistical analysis plan (SAP). The SAP will describe any predefined rules for including/excluding any subjects with data from any analyses (eg, time windows, visit by visit analysis, endpoint analysis, protocol violation).

9.3 Sample Size and Power Considerations

A total sample size of approximately 350 subjects (175 in the experimental arm [luspatercept (ACE-536)], 175 in the control arm [epoetin alfa]) will have 90% power to detect the difference between a RBC-TI (for 12 weeks associated with a concurrent hemoglobin increase) response rate of 36% in the experimental arm (luspatercept [ACE-536]) and a response rate of 20% in the control arm (epoetin alfa), with the first interim analysis on futility only when about 105 subjects have completed 24 weeks of treatment, or discontinued before reaching 24 weeks of treatment (30% information for primary endpoint). The Lan-DeMets (O'Brien-Fleming) spending function will

³ Instrument-dependent.

be used as the futility boundary. The sample size calculation is based on one-sided alpha of 0.025, test statistics on odds ratio of proportions using the EAST[®] Version 6.4 software system.

A second interim analysis to test the superiority of the luspatercept arm does not alter the above sample size calculation. The study power remains at 90% for the final analysis with 350 subjects and the Lan-DeMets spending function of the O'Brien-Fleming type will be used to control the overall one-sided Type I error rate at 0.025.

9.4 Randomization and Stratification

Subjects will be randomized to receive luspatercept or epoetin alfa at a 1:1 ratio.

Randomization will be accomplished by an IRT to ensure timely registration and randomization. A stratified randomization schedule will be implemented. Randomization will be stratified by baseline RBC transfusion burden, RS status, and endogenous serum erythropoietin (sEPO) level at baseline:

- RBC transfusion burden at baseline
 - < 4 pRBC units/8 weeks
 - ≥ 4 pRBC units/8 weeks
- Ring sideroblast (RS) status at baseline (with RS+ defined as ring sideroblasts ≥ 15% of erythroid precursors in bone marrow or ≥ 5% (but < 15%) if SF3B1 mutation is present).
 - RS+
 - RS-
- Endogenous Serum Erythropoietin (sEPO) level at baseline.
 - ≤ 200 U/L
 - > 200 U/L

9.5 Background and Demographic Characteristics

Subjects' age, height, weight, and baseline characteristics will be summarized using descriptive statistics, while gender, race and other categorical variables will be provided using frequency tabulations by treatment arm. Prior transfusion history will be summarized. Medical history data will be summarized using frequency tabulations by the Medical Dictionary for Regulatory Activities (MedDRA) system organ class and preferred term. Myelodysplastic syndrome (MDS) diagnoses as well as RBC transfusion dependence will be summarized using frequency tabulations.

9.6 Subject Disposition

Subject disposition (analysis population allocation, entered, discontinued, along with primary reason for discontinuation) will be summarized using frequency and percent for both treatment and follow-up phases. A summary of subjects enrolled by site will be provided. Protocol deviations will be summarized using frequency tabulations.

9.7 Efficacy Analysis

9.7.1 Primary Efficacy Analysis

The primary efficacy analysis will be the comparison of the response rates in the two treatment arms in the ITT population. The primary efficacy endpoint of RBC transfusion independence for 12 weeks with an associated concurrent mean increase of ≥ 1.5 g/dL Hgb increase, is defined as the absence of any RBC transfusion for any 12-week period from Week 1 to the end of Week 24 associated with a concurrent mean increase of hemoglobin of at least ≥ 1.5 g/dL compared to baseline.

For the primary efficacy endpoint, the response rate will be calculated using the number of responders divided by number of subjects in the ITT population (responders plus non-responders). The response rates of the subjects who were randomized to luspatercept and the epoetin alfa arm will be calculated. In the primary efficacy analysis, the statistical hypothesis is

$$H_0 : P_1 \leq P_2$$

$$H_a : P_1 > P_2$$

where P_1 denotes the true response rate in the luspatercept group, and P_2 denotes the true response rate in the epoetin alfa group. The number and percentage of subjects in the ITT population who achieve the response will be presented by treatment group. The Cochran–Mantel–Haenszel (CMH) test will be used to test the difference between the two response rates with randomization factors as strata. The one-sided significance level at the final analysis will be 0.021 with one planned interim analysis for superiority.

Additional details will be outlined in the SAP.

9.7.2 Secondary Efficacy Analyses

The secondary efficacy endpoints will be analyzed and reported at the time of the analysis of the primary efficacy endpoints.

Secondary endpoints will be analyzed descriptively, unless otherwise specified, and will be based on the ITT population. Kaplan-Meier methods will be used to estimate curves for time to event secondary variables. Count, percentages, and 95% confidence interval will be used to describe categorical secondary variables.

Gate-keeping method will be used to control the overall Type I error rate for the following secondary endpoints in the order of:

- HI-E response (Week 1 to 24)
- RBC-TI for 24 weeks (Week 1 to 24)
- RBC-TI ≥ 12 weeks (Week 1 to 24)

After the result from the primary efficacy endpoint shows statistical significance, RBC-TI for 24 weeks in Week 1 to 24 will be tested for significance at the one-sided significance level of 0.021 only if both primary endpoint and HI-E response in Week 1 to 24 are significant. RBC-TI ≥ 12 weeks in Week 1 to 24 will be tested for significance at the one-sided significance level of

0.021 only if the results for primary endpoint, HI-E in Week 1 to 24, and RBC-TI for 24 weeks in Week 1 to 24 are all significant. The testing procedure above will be implemented strictly in order to control the overall one-sided Type I error rate of 0.025 due to multiplicity.

Other secondary endpoints will be analyzed without employing methods for controlling the type one error rate. Any statistically significant treatment effect on these secondary endpoints cannot be interpreted as confirmatory, but rather informative.

RBC transfusion independence (RBC-TI) for 24 weeks is defined as the absence of any RBC transfusion from Week 1 to the end of Week 24. Subjects discontinued from the Treatment Phase prior to finishing Week 24 will be counted as non-responders.

Mean hemoglobin change over 24 weeks is defined as the mean hemoglobin change over the 24-week period of Week 1 through Week 24 compared to baseline

Hematologic improvement – erythroid response (HI-E) per IWG (Cheson, 2006) is defined as proportion of subjects meeting HI-E criteria sustained over any consecutive 56-day period over the first 24 weeks from Week 1. Subjects discontinued from the Treatment Period without achieving HI-E will be counted as non-responders.

Time to HI-E will be summarized only for subjects who achieve HI-E response. It is defined as time from Week 1 to first onset of achieving HI-E. It will be summarized only for subjects who achieve HI-E within the first 24 weeks from Week 1.

RBC-TI for ≥ 12 weeks (84 days) is defined as the proportion of subjects achieving RBC-TI for ≥ 84 days during any consecutive 84-day period from Week 1 through Week 24.

Duration of RBC-TI ≥ 12 weeks (84 days) is defined as the longest RBC-TI period for subjects who achieve RBC-TI ≥ 12 weeks from Week 1 through Week 24. Subjects who maintain RBC-TI through the end of the Treatment Period or at the time of analysis will be censored at the date of treatment discontinuation, date of analysis or death, whichever occurs first.

Time to RBC-TI ≥ 12 weeks (84 days) will be summarized only for subjects who achieve RBC-TI ≥ 84 days from Week 1 through Week 24. It is defined as the time between Week 1 and the date onset of TI is first observed (ie, Day 1 of 84 days without any RBC transfusions).

Time to first RBC transfusion is defined as time from Week 1 to first RBC transfusion on treatment. Subjects who maintain RBC-TI through the end of the Treatment Period or time of analysis will be censored at the date of treatment discontinuation/time of analysis or death, whichever occurs first.

RBC transfusion burden on treatment is defined as total number of pRBC units transfused within the first 24 weeks of treatment since Week 1.

RBC-TI for ≥ 56 days (8 weeks) is defined as the proportion of subjects achieving RBC-TI for ≥ 56 days during any consecutive 56-day period from Week 1 through Week 24.

RBC-TI for a consecutive 24-week period is defined as the proportion of subjects achieving RBC-TI for ≥ 168 days during any consecutive 168-day period from Week 1 through Week 48.

Progression to AML: time to AML progression is defined as the time between randomization and first diagnosis of AML as per WHO classification of $\geq 20\%$ blasts in peripheral blood or bone

marrow. Subjects with diagnosis of AML will be considered to have had an event. Subjects who have not progressed to AML at the time of analysis will be censored at the last assessment date which does not indicate progression to AML.

Overall survival (OS) is defined as the time between randomization and death/censored date. Subjects who die, regardless of the cause of death, will be considered to have had an event. Subjects who are alive at the time of analysis will be censored at the last assessment date at which the subject was known to be alive. All subjects who were lost to follow-up will also be censored at the time of last contact.

Full analysis details will be included in the SAP.

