Adult subjects (≥ 18 years) with anemia due to a IPSS-R very low, low, or intermediate risk MDS according to the WHO 2016 classification and a bone marrow blast count of $< 5\%$ (Arber, 2016; Greenberg, 2012), who are ESA naïve with endogenous sEPO levels of < 500 U/L and who require RBC transfusions (ie, 2 to 6 units/8 weeks of pRBCs confirmed for a minimum of 8 weeks immediately preceding randomization).

Length of Study

The expected duration of the study is approximately 8 years, which consists of approximately 2 years of enrollment, approximately 1 additional year of luspatercept or epoetin alfa treatment after the last subject is randomized, and 5 years of follow up from first dose of IP, or 3 years from last dose (whichever occurs later), to complete the Post-treatment Follow-up Period.

The End of Trial is defined as either the date of the last visit of the last subject to complete the post-treatment follow-up, or the date of receipt of the last data point from the last subject that is required for primary, secondary and/or exploratory analysis, as prespecified in the protocol, whichever is the later date.

The sponsor may end the trial when all key endpoints and objectives of the study have been analyzed and the availability of a roll-over protocol exists into which subjects remaining on study may be consented and continue to receive access to luspatercept and/or complete long-term follow-up. Such a protocol would be written for a compound that would not yet be commercially available.

Study Treatments

Eligible subjects will be randomized by a central randomization procedure using integrated response technology (IRT) at a 1:1 ratio to one of the below treatment arms:

- **Experimental Arm:** luspatercept (ACE-536): starting dose of 1.0 mg/kg subcutaneous injection every 3 weeks (21 days; Q3W). Dose levels can be increased in a stepwise manner beyond the starting dose to 1.33 mg/kg, and up to a maximum of 1.75 mg/kg .

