Primary	Red blood cell transfusion independence (RBC-TI) for 12 weeks (84 days) with a mean hemoglobin increase ≥ 1.5 g/dL	Proportion of subjects who are RBC transfusion-free for any 12-week period associated with a concurrent mean hemoglobin increase ≥ 1.5 g/dL compared to baseline	Week 1 through Week 24
Secondary	Red blood cell transfusion independence (RBC-TI) for 24 weeks	Proportion of subjects who are RBC transfusion-free from Week 1 through Week 24	Week 1 through Week 24
	Mean hemoglobin change over 24 weeks	Mean hemoglobin change over the 24-week period of Week 1 through Week 24 compared to baseline	Week 1 through Week 24
	Hematologic improvement – erythroid response (HI-E) per IWG (Cheson, 2006)	Proportion of subjects achieving HI-E over any consecutive 56-day period	Week 1 through Week 24
	Time to HI-E	Time from first dose to first onset of achieving HI-E	Week 1 through Week 24
	RBC-TI for ≥ 12 weeks (84 days)	Proportion of subjects who are RBC transfusion-free over a consecutive 84-day period	Week 1 through Week 24
	Duration of RBC-TI ≥ 12 weeks (84 days)	Maximum duration of RBC transfusion independence for subjects who achieve RBC-TI ≥ 84 days	Week 1 through End of Treatment
	Time to RBC-TI ≥ 12 weeks (84 days)	Time from first dose to first onset of transfusion independence ≥ 84 days	Week 1 through Week 24
	Time to first RBC transfusion	Time from first dose to first transfusion on treatment	Week 1 through End of Treatment
	RBC transfusion burden on treatment	Total number of RBC units transfused on treatment	Week 1 through Week 24
	RBC-TI for ≥ 56 days (8 weeks)	Proportion of subjects who are RBC transfusion-free over a consecutive 56-day period	Week 1 through Week 24
	RBC-TI for a consecutive 24-week period	Proportion of subjects who are RBC transfusion-free for a consecutive 24-week period in the first 48 weeks from first dose	Week 1 through Week 48
	Health-related quality-of-life (HRQoL)	Evaluation of EORTC QLQ-C30 score and FACT-An	Screening through Week 24
	Safety	Type, frequency, severity of AEs and relationship of AEs to luspatercept/epoetin alfa	Screening through 42 days post last dose; Randomization through Week 48

Table 2: Study Endpoints

Endpoint	Name	Description	Timeframe
Secondary (continued)	PK parameters	Serum luspatercept concentrations and PK parameters	Randomization through 1 year post first dose
	Antidrug antibodies (ADA)	Frequency of antidrug antibodies	Randomization through 1 year post first dose

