6.4.1 Transfusion Assessment

The RBC transfusion data during the 8 weeks immediately preceding randomization will be used to determine the baseline RBC transfusion requirement for an individual study subject.

During the Treatment Phase transfusions will be assessed and recorded in the eCRF on an ongoing basis (prior to each dose of IP) until 8 weeks after last dose of IP or the End of Treatment Visit, whichever occurs later. Clinical site staff must confirm (and document in the subject's source record) if any transfusions were received by the subject (including any transfusions received at institutions outside of the study site in between study visits) prior to each IP administration. In addition to local procedures in place at the site to capture this information, a patient transfusion diary will be provided to subjects and will be reviewed by the site when/if returned by the patient.

Red blood cell transfusions administered for elective surgery, infections or bleeding events will not count toward baseline requirement, efficacy assessment, or progressive disease status but should still be recorded in the eCRF.

The following information will be collected for RBC transfusions (and platelet transfusions if applicable) and reported in the eCRF:

- Type, number of units, reason and date of transfusion
- The Hgb value for which any RBC transfusion is given, and the platelet value for which any platelet transfusion is given, (these Hgb and platelet values may be local or central laboratory measurements)

Please find recommendations for adequate source documentation of transfusion history as well as transfusions given during the treatment phase below:

- Signed original or copy of single transfusion record including number of units administered and Hgb/platelet value prior to transfusion.
- Signed record of multiple transfusions done at the same clinic. For each transfusion, the units and dates are specified along with Hgb/platelet value prior to each transfusion.

- If electronic record: signed print-out of administration record(s), specifying unit(s) on specified date(s), plus signed additional documentation of Hgb/platelet values(s) prior to transfusion.
- Signed referral letter(s) specifying date(s) and number(s) of units administered with Hgb/platelet value(s) prior to transfusion(s).

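### The Week 1 to 48 transfusion-independence endpoint falls due for reporting at a 24-week data cut, with no rule for subjects short of 48 weeks

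*Combined protocol and SAP*

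**What the plan says.** - **Reporting time.** Section 9.7.2: "The secondary efficacy endpoints will be analyzed and reported at the time of the analysis of the primary efficacy endpoints". No endpoint is exempted. The same section makes the ITT population the basis for secondary endpoints.
- **Trigger.** Section 9.1: "The final analysis will be performed when all randomized subjects have completed 24 weeks of treatment or discontinued before 24 weeks".
- **Endpoint.** Section 2, Table 2: "Proportion of subjects who are RBC transfusion-free for a consecutive 24-week period in the first 48 weeks from first dose". Section 9.7.2 requires at least 168 transfusion-free days "during any consecutive 168-day period from Week 1 through Week 48".
- **Data-cut rules elsewhere.** For duration of RBC-TI, Section 9.7.2 says: "Subjects who maintain RBC-TI through the end of the Treatment Period or at the time of analysis will be censored". Time to first transfusion has a similar rule. Non-responder rules for discontinued subjects are written for RBC-TI over Weeks 1 to 24 and for HI-E. The Week 1 to 48 proportion has neither kind of rule.
- **Superiority interim.** Section 9.9 sets it at about 300 subjects who have completed 24 weeks or stopped earlier. It also says the remaining secondary endpoints will be analyzed then, without Type I error control.
- **Later analysis.** Section 9.1: "Additional follow-up analysis for efficacy and safety will be performed when all subjects have been followed for 5 years" from first dose, or 3 years from last dose if that is later. This endpoint is not named there.

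**The concern.** The cut that suits a 24-week endpoint comes too early for a 48-week one. Every other proportion in Section 9.7.2 uses a window that closes at Week 24. This one closes at Week 48, so subjects randomized late contribute less observation time to a fixed-window proportion.

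The subjects at risk of being missed are those whose 24-week run starts after Week 1, and they are exactly what this endpoint adds to RBC-TI over Weeks 1 to 24. The titration rules make such runs plausible. Under Section 7.2.1.2 the highest luspatercept level can be reached at Week 13 at the earliest, and a 24-week run starting then ends at Week 36. Under Section 7.2.2.2 the highest epoetin alfa level can be reached at about Week 11, and such a run ends at about Week 34.

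At stake is whether the first reported figure, given with a 95% confidence interval, is the endpoint that Table 2 defines.

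**Working it through.** **Inputs.** N = 350 (Section 9.3), interim at 300 subjects (Section 9.9), and enrollment of about 2 years (Protocol Summary, Length of Study). The plan states no figure for this endpoint, so there is none to reproduce. Uniform enrollment is an assumption. Durations of 3 and 4 years are also shown, because the rationale for Amendment 4.0 reports that the pandemic harmed enrollment. The gap of up to 3 days between randomization and first dose is ignored.

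**Step 1: subjects short of 48 weeks at the final cut.** With enrollment lasting A weeks, the cut falls at week A + 24. A subject randomized at week u has A + 24 − u weeks of potential follow-up, which is under 48 when u > A − 24. The share is therefore 24/A.

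**Step 2: understatement.** Let p24 be the true proportion for RBC-TI over Weeks 1 to 24, and p48 the true proportion for this endpoint. The documents give neither, so gaps of 5, 10 and 20 points are assumed. Late responders are those who complete their run between Weeks 24 and 48. If they complete it uniformly over that period, and truncated follow-up is uniform on 24 to 48 weeks, half of the late responders among truncated subjects are unseen:

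loss = (24/A) × (p48 − p24)/2

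| A (weeks) | 24/A | Short, of 350 | Loss, 5-point gap | 10-point gap | 20-point gap |
|---|---|---|---|---|---|
| 104 | 0.231 | 80.8 | 0.58 | 1.15 | 2.31 |
| 156 | 0.154 | 53.8 | 0.38 | 0.77 | 1.54 |
| 208 | 0.115 | 40.4 | 0.29 | 0.58 | 1.15 |

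Example: a true 40% with p24 = 30% would be reported as 40 − 1.15 = 38.8% (2 years) or 40 − 0.58 = 39.4% (4 years).

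A simulation of 4 million subjects with p48 = 40% and the same three gaps lost 0.59, 1.16 and 2.32 points at A = 104, and 0.27, 0.58 and 1.16 at A = 208. Restricting to subjects randomized at least 48 weeks before the cut returned 40.0%.

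**Step 3: sensitivity to when late runs complete (A = 104).** The share of all late responders left unseen is 5.8% if runs complete early, 11.5% if uniformly and 17.3% if late. A 10-point gap then costs 0.6, 1.15 or 1.7 points.

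**Step 4: superiority interim (A = 104).** Take the 300 as the first 300 randomized.
- The 300th is randomized at week 104 × 300/350 = 89.1, so the cut is at week 113.1.
- Subjects with at least 48 weeks were randomized by week 65.1: 350 × 65.1/104 = 219.
- Short: 300 − 219 = 81 of 300 (27%), or 350 − 219 = 131 of 350 (37%) if all randomized subjects are in the denominator.
- Loss on the 300: 0.269 × gap/2 = 0.67, 1.35 or 2.69 points for gaps of 5, 10 or 20.
- With 3 or 4 years of enrollment, 54 (18%) or 40 (13%) of the 300 are short.

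All counts are upper limits. Subjects who discontinued before the cut are not truncated by it, and some who are short of 48 weeks will already have a qualifying run.

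**The case against.** **The SAP may cover it.** Section 9.2 leaves missing-data methods and rules for including or excluding subjects to the SAP, and Section 9.7.2 ends by referring full details there. No SAP text in the document supplied gives a rule for this endpoint, so a separate SAP could supply a counting rule. It could not move the report later without contradicting the timing sentence in Section 9.7.2.

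**A later efficacy analysis is planned.** By then every subject has passed Week 48 or left, and the complete proportion could be shown. That is years later, and this endpoint is not named.

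**Too low is an inference.** Counting truncated subjects as non-responders is not written for this endpoint. It follows from an ITT denominator with no other rule. The contrast with the censoring rules is limited, since those concern time-to-event variables.

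**The size is modest.** Section 1.2.2 reports erythroid responses within the first 3 months in a substantial proportion of luspatercept-treated MDS subjects, which favors the early-completion case: about half the losses in the main table. That evidence covers one arm only. For a 40% rate with 175 per arm, the 95% half-width is 1.96 × √(0.4 × 0.6/175) = 7.3 points for one arm and 1.96 × √(2 × 0.4 × 0.6/175) = 10.3 for the difference. Truncation by calendar date should also be similar in both arms under 1:1 randomization.

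**The interim limb is weaker.** Table 9 lists only the primary and the three gated endpoints. The text of Section 9.9 nevertheless says the others will be analyzed.

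These points limit the consequence. They do not remove the conflict between the timing rule and the endpoint definition.

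**Conclusion.** The concern holds. Followed literally, Sections 9.1 and 9.7.2 report a 48-week proportion before its window has closed for every subject, and that proportion is understated.

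Under uniform 2-year enrollment, up to 81 of 350 subjects (23%) are affected at the final cut, with a loss of about 0.6 to 2.3 points for an assumed late-response gap of 5 to 20 points and uniform completion of late runs. With 4 years of enrollment, the figures are up to 40 subjects (12%) and 0.3 to 1.2 points. The effect on the between-arm difference depends on late response in each arm, and its direction is not established.

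The endpoint is descriptive and ungated, so Type I error, power and sample size are unaffected. The change should be made so that the reported figure matches its definition.

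**What to change.** Amend Section 9.7.2, and the SAP to match:

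1. Exempt RBC-TI for a consecutive 24-week period from the rule tying secondary endpoints to the primary analysis. Report it when all randomized subjects have reached Week 48 or discontinued.
2. If a figure is shown at the interim or final cut, restrict numerator and denominator to subjects randomized at least 48 weeks before the cut, including those who discontinued, and label it so.
3. State how subjects who discontinue before Week 48 without a 168-day run are counted. Transfusion collection ends 8 weeks after the last dose or the End of Treatment Visit, whichever is later, so their 48-week record may be incomplete.

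**Cost.** Wording and one later table run. No new data are needed: Section 6.4.1 says "transfusions will be assessed and recorded in the eCRF on an ongoing basis" during treatment, and the Length of Study text plans "approximately 2 years of enrollment, approximately 1 additional year of luspatercept or epoetin alfa treatment after the last subject is randomized". The complete figure arrives about 24 weeks later. With 2-year enrollment, a restricted early figure would rest on about 350 − 81 = 269 subjects at the final cut, or 219 at the interim.
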